6. INVESTIGATIONAL MEDICINAL PRODUCT AND PLACEBO 6.1 STUDY DRUG

6.1.1 Study Drug Identification

6.1.1.1 Dexamethasone solution for injection

Several generics available in 1mL or 2mL ampoules / vials and in packs of 10 exist for Dexamethasone. As there are different salts available for dexamethasone, it should be prescribed as dexamethasone (base) 16.5mg for 5 days, then 8.25mg for 5 days.

Each site hospital pharmacy should plan to supply stock according to their local practices Site pharmacists should maintain communication with site investigators regarding available stock, to ensure that participants are only enrolled when sufficient stock is available. As IMP will be taken from local clinical stock accountability will be risk adapted, there is no requirement for trial specific accountability. Sites may document accountability in accordance with local policy/practice but this will not be monitored by the Sponsor.

6.1.2 Study Drug Manufacturer

Any preparation of dexamethasone solution for injection which has marketing authorisation in the UK and is stocked by the site hospital pharmacy, may be employed in this trial.

6.1.3 Marketing Authorisation Holder

The site hospital pharmacy can supply any generic of dexamethasone solution for injection available to them for the purposes of this trial. An example of this include:

Dexamethasone (base) 3.3mg per mL solution for injection MA Holder is hameln pharma ltd, [name], UK and the MA number is PL 01502 /0079.

6.1.4 Labelling and Packaging

The trial has been classified as a Type A risk adapted CTIMP as any potential risk is no higher than that of standard medical care. No specific arrangements are planned for labelling since all dexamethasone injection used in this trial will be licensed medicinal products that are currently commercially available in the UK.

The IMP will not require a study specific label as they will be taken from stock already stored in the Intensive Care Unit The drug will be prescribed by those experienced in doing so in these circumstances and it is used within the broadly licenced indications.

6.1.5 Storage

Storage and supply of the IMP will be undertaken by the site as per the standard local procedures. IMP will be stored as per the clinical stock used by the Intensive Care Unit at the local site, this may be stored in pharmacy, the Intensive Care Unit or other ward level location according to standard site practice.

Storage conditions for dexamethasone injections should be as per Summary of Product Characteristics (SmPC) for that product. Briefly, Dexamethasone (base) 3.3mg/1mL solution for injection should not be stored above 25°C. Do not freeze.

The product should be used immediately after opening but if it is not, it may be refrigerated (2 to 8°C) and used within 24 hours.

As IMP will be taken from local clinical stock, storage monitoring requirements are risk adapted, temperature monitoring will be as per local site practice. No reporting of temperature excursions to the Sponsor is required. As stock is off the shelf it is usual to follow local practice for dealing with temperature excursions in drug storage areas.

6.1.6 Regulatory Release to Site

Not applicable. Dexamethasone injections used in this trial are commercially available licensed products.

6.1.7 Destruction of Trial Drug

As dexamethasone will be taken from routine clinical stock and only be administered to participants while they are in-patients in ICU there will not any drug returned to site pharmacies. Opened ampoules will be destroyed at ward level. Site pharmacies should follow their local practice / policies for drug destruction and documentation. No approval from Sponsor is required.

6.1.8 Summary of Product Characteristics (SPC) Booklet or Investigators Brochure

The dexamethasone (base) 3.3mg/1mL injection Summary of Product Characteristics (SPC) (hameln pharma ltd, [name], UK) is provided in a separate document with a cover sheet and signature page (signed and verified by the Cl and Co-Sponsors) and is filed in the TMF. This is a representative SPC used widely within the NHS.

6.2 PLACEBO

As an open label RCT, there is no placebo preparation in this trial.

6.3 DOSING REGIME

Each participant randomised to the intervention arm will be administered Dexamethasone base 16.5mg (equivalent to Dexamethasone Phosphate 20mg) on days 1 to 5 followed by Dexamethasone base 8.25mg (equivalent to Dexamethasone Phosphate 10mg intravenously once a day on days 6 to 10. The daily doses will be administered once a day at approximately the same time each day.

Dexamethasone solution for injection can be given without mixing or dilution. When dexamethasone solution for injection is given by intravenous infusion, glucose 5% in water and sodium chloride 0.9% have been recommended as diluents, as per site practice. Critical Care nurses with appropriate training will prepare and administer dexamethasone as per standard site practice. No weaning off the dexamethasone dose is required after the 10 days treatment period.

6.4 DOSE CHANGES

There will be no change to the dosing regimen detailed in 6.3 where patients are in the ICU/HDU. If patients are discharged from ICU/HDU before the 10-day intervention period is complete dexamethasone treatment will stop. If this occurs, participants will continue in the trial and all follow-up data will be collected where possible.

6.5 PARTICIPANT COMPLIANCE

Dexamethasone will be prescribed on the participants' in-patient drug administration chart (or equivalent) and administered to the participant by appropriately trained clinical staff in accordance with local practice. All doses given will be recorded on the chart and reasons for a dose being missed will be documented as per routine practice. The timing of each dose and compliance will be recorded in the trial database, and reasons for missing will be captured.

6.6 OVERDOSE

As the maximum daily dose is 16.5mg (as base) and is administered by appropriate clinical staff, who are trained and experienced in administering medicinal products, overdose is extremely unlikely. Reports of acute toxicity and/or deaths following overdosage with glucocorticoids are rare. No antidote is available so in the case of an overdose symptomatic treatment should be administered as per local policy.

6.7 OTHER MEDICATIONS

6.7.1 Non-Investigational Medicinal Products

Not applicable. There are no non-investigational medicinal products in this trial.

6.7.2 Permitted Medications

All other interventions will be allowed as per the clinical team including those affecting CYP3A4, because it is not clinical practice at the trial sites to change the use or dosing of

dexamethasone with concomitant use of CYP3A4 inhibitors or inducers. Concomitant administration of neuromuscular blocking agents (such vecuronium, rocuronium) could increase the risk of critical illness related muscle weakness. However, it is well recognised that patients with ARDS may require concomitant administration of these drugs to provide respiratory support, and therefore permitted³. Interactions with other medicinal products are contained in the SPC Section 4.5.

6.7.3 Prohibited Medications

Contraindications: Glucocorticoids which are used for a proven indication excludes the patient from this trial. There are no known contra-indications to short-term corticosteroid use. Dexamethasone interacts with several medicinal products detailed in the SPC Section 4.5 which should be considered.

7. STUDY ASSESSMENTS

7.1 SAFETY ASSESSMENTS

We will capture two key safety events – nosocomial infections, and clinically important upper gastrointestinal bleeding (UGI bleeding). Rationale being these two events are (a) recognised severe side effects of glucocorticoid treatment, and (b) critically ill patients are at risk of these two events. Nosocomial infections will be defined using the proxy of antibiotic free days during critical care stay, by collecting number of days of antibiotic therapy. Clinically important UGI bleeding will be defined as overt GI bleeding (defined as hematemesis, melena, or frank blood in the nasogastric tube or endoscopy confirmed bleeding due to peptic ulceration), needing transfusion of two or more units of packed red blood cells³². For these safety events, we will record the date/time of all events up to day 60 or until ICU stay if earlier than 60-days. Serious adverse events, and adverse events (SAE/AE reporting) will be captured and reported in addition to above outcomes, as per Sponsor guidance.

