	At 180-days All-cause mortality; Health-related quality of life; Health Service Use Follow-up
IMP(s)	Dexamethasone
IMP Route of Administration	Intravenous

Background to the trial:

Every year about 120,000 adults who are admitted to Intensive Care Units (ICUs) require a machine, called a ventilator, to help them breathe. In patients who need ventilation, about 1 in 4 have a life-threatening condition with severe breathing difficulties called acute respiratory distress syndrome (ARDS). Unfortunately, around 40% of patients with ARDS die within 60 days of developing this condition.

Breathing difficulties in ARDS happen because the lungs fill with fluid due to inflammation, which is part of the body's response to the conditions causing ARDS. Over the last 30-years, various drug treatments have been tested to reduce the inflammation in ARDS, with little success. At present, there are no drugs that cure ARDS. However, in 2020, a small research study (the DEXA-ARDS trial) in Spain looked at dexamethasone as a treatment for ARDS.

Dexamethasone is a well-known steroid, which is a cheap antiinflammatory drug that is already widely used to treat other illnesses (such as arthritis and asthma). The result of DEXA-ARDS trial showed that it may help patients survive ARDS. These results from Spain are hopeful but to help us know how effective dexamethasone is, we need to test it in a much larger group of patients who come into the NHS with ARDS. We are planning to conduct a large clinical trial across the UK.

Lay Summary of Trial

Aim(s) of the trial:

The aims of our study is to find out if dexamethasone treatment in patients with ARDS can save lives, reduce the need for extended ICU care, improve longer term patient quality of life and find the best value for the public and health services.

Design:

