Severe ARDS patients have a median (inter-quartile range (IQR)) duration of mechanical ventilation of 9 (4-16) days, ICU length of stay of (LOS) of 11 (5-19) and hospital LOS of 16 (6-31) days⁴. Further, patients with ARDS utilise considerable ICU/hospital capacity and cost (Cost per NHS ICU bed-day = £1932; ward= £413; mean estimated cost of ICU stay based on a UK RCT involving ARDS patients⁷ was £26,857 (95 % CI £25,222–£28,491))⁸. Given the long-term sequalae described above, ARDS survivors continue to need primary care contact and ongoing rehabilitation in the community. The mean societal cost at 1 year exceeds £40K, and the total societal cost divided by the number of 1-year survivors is estimated to exceed £90K⁷.

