4.3 EXCLUSION CRITERIA

- (a) ARDS due to microbiologically confirmed SARS-Co-V2 infection (COVID-19 ARDS)
- (b) Major upper gastrointestinal bleeding during current hospital admission, defined as requiring endoscopy and transfusion for two or more units of packed red blood cells. This exclusion criterion will exclude patients with contraindications to the glucocorticoids on the grounds of safety.
- (c) High dose glucocorticoids are required for a separate proven clinical indication at the time of randomisation as withholding treatments that have been deemed clinically effective, would be unethical.

Note: Low dose glucocorticoid treatments for clinical indications (defined as maximum daily dose of 200mg hydrocortisone or equivalent other steroids) is not an exclusion criterion.

- (d) Known hypersensitivity to dexamethasone³¹
- (e) Infections that are not being effectively treated as determined by the treating medical team
 - **Note:** Once infections are considered as effectively treated by the treating medical team, they are eligible for the trial.
- (f) Planned intensive care treatment withdrawal within next 24 hours as determined by the treating medical team
- (g) Patients who are known to be pregnant
- (h) Previous enrolment in the GuARDS trial

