8.2 Daily data during ICU stay

Mechanical ventilation status, information about organ support as defined by the UK Critical Care Minimum Data Set; drug-related adverse events (upper GI bleed and days of antibiotic therapy); ICU length of stay; secondary outcome variables.

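### Nosocomial infection, one of two key safety events, is measured as antibiotic-free days within the ICU stay, a count that moves with length of stay and responds only weakly to new infection

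*Protocol*

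**What the plan says.** Protocol section 7.1 selects nosocomial infection and upper gastrointestinal bleeding as the two key safety events, because both are recognised severe effects of glucocorticoids and critically ill patients are at risk of them. Bleeding gets clinical criteria. Infection gets a proxy: "Nosocomial infections will be defined using the proxy of antibiotic free days during critical care stay", obtained "by collecting number of days of antibiotic therapy". For both events the section adds that "we will record the date/time of all events up to day 60 or until ICU stay if earlier than 60-days".

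Sections 7.2 and 8.2 list days on antibiotics among the daily ICU data. Neither adds an onset date, an indication, microbiology or a rule for telling a new infection from the presenting one.

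Three other places bear on the point:
- Section 1.1.1 lists pneumonia, non-pulmonary infection and sepsis among the causes of ARDS. Exclusion criterion (e) in section 4.3 removes only "Infections that are not being effectively treated as determined by the treating medical team", and its note makes patients eligible once the infection is effectively treated.
- Duration of ICU stay is a secondary endpoint (section 2.2.2, Table 1), and the lay summary gives as one aim to "reduce the need for extended ICU care".
- AE and SAE recording ends at day 21, death or ICU discharge, whichever comes first (section 11.2). Section 11.3.2 exempts known dexamethasone side effects and events in keeping with critical illness, unless judged related to trial participation.

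**The concern.** A count of antibiotic-free days inside the ICU stay is ICU days minus antibiotic days. Its ceiling is the stay itself, so quick recovery and early death both lower it and a long stay raises it. The trial hopes to change stay and mortality, so the safety measure is tied by construction to the expected treatment effects.

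Antibiotics for the presenting infection enter the same count. Randomisation balances that component on average, so it mainly dilutes the contrast. Directional error comes from differences in stay and death, and possibly from open-label prescribing.

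At stake is how the trial's infection-safety result is read. A drug that shortens ICU stay without affecting infection could look harmful, and one that raises infection while lengthening stay could look safe. Section 1.2.1 gives sparse trial data on glucocorticoid harms as part of the case for the trial. The AE route is only a partial backstop, so an ordinary ICU-acquired pneumonia may not be identified elsewhere.

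**Working it through.** The protocol gives no rate, effect or power for this outcome, so there is no figure to reproduce. The check asks how the proxy behaves when infection and stay change separately.

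**Arithmetic of the count.** Free days = ICU days − antibiotic days. Take the protocol's ICU-stay quartiles for severe ARDS (5 and 19 days, section 1.1.1) and assumed courses. A patient who leaves on day 5 after antibiotics throughout scores 5 − 5 = 0. A patient who stays 19 days, with a 7-day course for the presenting infection and another 7-day course for a new pneumonia, scores 19 − 14 = 5. The patient with the nosocomial infection scores better. These two patients illustrate the mechanism; they are not an arm contrast.

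**Arm contrast by simulation (1,000,000 patients per arm).**

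From the protocol: median ICU stay 11 days, quartiles 5 and 19. Lognormal fit: sigma = ln(19/5) / (2 × 0.6745) = 0.99, giving fitted quartiles of 5.6 and 21.4. Stay is rounded up to whole days and capped at day 60.

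Assumed, not in the protocol:
- 70% have a presenting infection (50% and 90% also tried);
- 7-day courses for presenting and new infections;
- new-infection hazard 0.015 per ICU day, multiplied by 1.0 or 1.3;
- stay multiplied by 0.8, 1.0 or 1.2;
- each new infection adds 0 or 10 ICU days.

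Death is not modelled separately.

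Results at 70% presenting infection:

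| Scenario | Mean ICU days | Antibiotic days | Free days | % with new infection | First new infections per 1000 ICU days at risk |
|---|---|---|---|---|---|
| Control | 16.83 | 5.31 | 11.5 | 20.5 | 14.9 |
| A: same hazard, stay ×0.8 | 13.94 | 4.91 | 9.0 | 17.4 | 14.9 |
| B: hazard ×1.3, same stay | 16.83 | 5.51 | 11.3 | 25.2 | 19.3 |
| C: hazard ×1.3, stay ×0.8 | 13.97 | 5.07 | 8.9 | 21.6 | 19.3 |
| D: hazard ×1.3, stay ×1.2 | 19.45 | 5.87 | 13.6 | 28.5 | 19.3 |
| Control, infection adds 10 days | 18.59 | 5.54 | 13.0 | 20.6 | 14.9 |
| E: hazard ×1.3, infection adds 10 days | 18.98 | 5.81 | 13.2 | 25.2 | 19.2 |

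Reading the rows against control (E against its own control):
- A: 11.5 − 9.0 = 2.5 free days lost, an apparent harm, although the hazard is unchanged and fewer patients are infected.
- B: the direction is right, but a 30% higher hazard moves the proxy by 11.5 − 11.3 = 0.2 days.
- C: the proxy is almost the same as in A (8.9 v 9.0), so it barely distinguishes a true 30% rise from none. The raw antibiotic-day count falls from 5.31 to 5.07 although the hazard is higher.
- D: free days rise by 13.6 − 11.5 = 2.1, an apparent benefit, although more patients are infected.
- E: the sign is wrong, though by only 0.2 days, because infection itself lengthens stay.

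Within an arm, free days correlate 0.96 to 0.97 with length of stay, and positively (0.24 to 0.48) with having a nosocomial infection. With 50% or 90% presenting infection the directions are the same: control 12.7 and 10.3 free days, A 10.2 and 7.9, D 14.8 and 12.4.

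**Does dividing by ICU days repair it?** Antibiotic days per 100 ICU days: control 5.31/16.83 = 31.6; A 4.91/13.94 = 35.2; B 5.51/16.83 = 32.7; D 5.87/19.45 = 30.2. A still looks harmful and D still looks beneficial, because presenting courses fall early in the stay.

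The rate of first new infection per ICU day at risk gives a ratio of 19.3/14.9 = 1.30 in B, C and D and 1.0 in A. That recovery is expected, since the simulated hazard is constant and every new infection is identified.

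**The case against.** The strongest reply is that section 7.1 names a proxy and a data source but no between-arm statistic, denominator or handling of death. Those can go into the SAP, and ICU stay is collected. This stands in part: the SAP may choose the summary. But the protocol itself fixes the definition and the window, and rescaling antibiotic days by ICU days does not remove the reversals in A and D.

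A reader might infer that new and presenting infections can never be separated. The documents do not support that. Antibiotic therapy is listed among daily ICU data, so if status is entered day by day a restart after a gap could be derived. What is missing is any rule that makes such a restart the event.

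A reader might also infer that most antibiotic days belong to the presenting illness. The protocol gives no share. In the simulation it was 68% to 89%, but that follows from assumed inputs.

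Other limits are fair. The ICU-stay quartiles describe severe ARDS in a cited cohort, while the trial enrols moderate to severe disease. The measure is openly called a proxy, is neither the primary nor a listed secondary endpoint, and plays no part in the stopping boundaries. A data monitoring committee oversees safety, and fatal infection counts in all-cause mortality. These bound the consequence but do not make the proxy a readable measure of infection.

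**Conclusion.** The point holds as a weakness in how one key safety event is measured. As defined, the proxy mainly reflects length of ICU stay. Under the stated assumptions, a 20% difference in stay moves it by 2 to 2.5 days, against 0.2 days for a 30% higher infection hazard at equal stay. A day count also has no event date, so it cannot deliver the dates and times promised in section 7.1.

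It would go too far to say that the proxy will point the wrong way. Reversal needs a difference in stay between arms, or infections that lengthen stay; with equal stay the direction is right. The sizes rest on assumed infection shares, course lengths, hazards and changes in stay. The directions were the same at all three infection shares tried. Death in ICU, which also truncates the count, was not quantified. The primary outcome and sample size are untouched. This is a cheap improvement, worth making because the trial is meant to inform on harm.

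**What to change.** In section 7.1, define the infection event as the first new antimicrobial course started more than 48 hours after randomisation, not counting switches or de-escalation of an ongoing course. Record its start date on the daily ICU form.

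Report two summaries by arm: the rate per ICU day at risk (cause-specific hazard), and the cumulative incidence with death and ICU discharge as competing events. Both are needed, because cumulative incidence alone also moves with stay (17.4% v 20.5% in scenario A at the same hazard). Keep antibiotic days as a descriptive measure, shown per ICU day and not read as infection.

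A fixed 28-day count of antibiotic-free days with death scored 0 may seem an easy alternative but is not advised. It brings the mortality effect into the infection measure: if the planned 8% absolute reduction were present by day 28 and survivors averaged 21 free days (assumed), dexamethasone would gain 0.08 × 21 = 1.7 days with no effect on infection. It also needs antibiotic data after ICU discharge, while the planned daily collection covers the ICU stay.

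Cost: one extra field and a few sentences in the protocol and SAP. Suspected as well as confirmed infections are counted, and open-label prescribing can still influence the measure. Both limits apply to the present proxy too.

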7.2 STUDY ASSESSMENTS

See Table 3 for a summary of all study specific assessments.

Baseline data will be recorded (Age, sex, height, index of multiple deprivation, self-reported ethnicity, smoking status in the past 6 months, hospital site, pre-existing co-morbidity; ARDS risk factor, APACHE II score; Sequential Organ failure Score; mode of ventilation and ventilator settings, measure of ARDS, use of adjunctive therapies. Baseline data thus includes key intersectional data considered within the NIHR-INCLUDE roadmap. This will enable us to monitor inclusion of under-served groups in the trial.

Daily data during ICU stay to report secondary outcomes will be recorded for all patients (mechanical ventilation status; respiratory, renal, cardiovascular organ support as defined by the UK Critical Care Minimum Data Set; length of stay (ICU (includes HDU), and hospital); non-trial glucocorticoid treatment; safety outcomes (upper GI bleed and number of days of antibiotic therapy); and adverse events as per the adverse event reporting guidance.

7.3 COMPLIANCE ASSESSMENTS

Protocol compliance will be monitored. Please also see section 6.5 for IMP compliance information.

7.4 LONG TERM FOLLOW UP ASSESSMENTS

Long term follow-ups will be checked at site. The primary objective of mortality will be checked at 60d post randomisation. At this time the HRQol will be measured using EQ-5D. Patients will be asked to complete a HRQol questionnaire at 60, 90 and 180 days post randomisation. These questionnaires will be completed in person, via phone or email. Long-term follow up data on health care use will be obtained with data linkage as described in Section-8. A health resource use questionnaire will be carried out by a phone call with the patient at 60, 90 and 180 days by a member of the research team.

Table 3: Schedule of events

Events and Procedures	Screen ing (Day 0)	Randomisat ion (Day 1)	Day 2-5	Day 6-10	ICU Stay	In hospital stay	Day 60	Day 90	Day 180
Study Procedures									
Informed consent	Х								
Medical History	Х								
Review and confirm eligibility	X								
Demographics	X								
Baseline data	X								
Research blood		Х ^а	\mathbf{X}^{b}						
samples		^	^						
Intervention									
Usual Care or									
Dexamethasone		Х	Х	X					
Treatment									
Efficacy Measures									
First successful					Х	X			
extubation									
Mechanical Ventilation		х	Х	Χ	Х				
status									
Organ support		X	Х	Х	Х				
information									
AE/SAE Recording		Х	Χ	Χ					
Duration of stay					Х	Х			
Long Term Follow-up									
HRQoL							Χ	Х	Χ
Mortality							Χ	Х	Χ
Health Resource Use							X	Х	Χ

^a Prior to first dose of the intervention

